#### **10.3.10 Adverse Events**

All events meeting the definition for AE, SAE, and pregnancy will be assessed and reported following guidelines provided in [Section 11.0](#). At Day -1, during the confinement period at regular intervals, and at follow-up, subjects will be asked about any new or ongoing AEs since the previous inquiry. Four weeks after last dose of tracer administration, an inquiry via phone will be done for the identification of potential SAEs.

Clinically significant changes from baseline in any safety or clinical laboratory parameter will be recorded as AEs or SAEs, if deemed appropriate by the Investigator.

Subjects who discontinue due to a treatment-emergent SAE will be followed-up by the Investigator until the SAE has resolved ([Section 7.6.1](#)).

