### **Trial Procedures and Assessments**

After assessing eligibility during a 3-week screening period, up to 10 healthy male subjects or female subjects will participate in the study. Subjects will be admitted to the study center on Day -1, the day before (first) tracer administration for baseline assessments and to (re-)confirm eligibility. Subjects will stay in the clinical unit for 5 days (4 nights) for imaging sessions 2 and 3. For the baseline PET scan, subjects may leave the unit in the evening. Blood samples for PK analysis will be collected pre-dose and at specified time points up to Day 4 post-dose (sessions 2 and 3). Physical examinations, vital signs, ECG, will be performed at specified times. Adverse events will be recorded throughout the study. A follow-up visit will take place 7 days ( $\pm$ 3 days) after receiving the last tracer dose. For details regarding the timing of specific procedures, see [Table 1](#).

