- Screening Assessments:** Screening will be within 21 days before imaging session 1.
- Imaging Admissions:** Admission for imaging session 2 will be within 7 days after the baseline PET scan; and admission for imaging session 3 will be within 7–14 days after imaging session 2.
- PET Repeat/Reschedule:** In the case of technical failures (i.e., such as unsuccessful tracer synthesis or a PET scanner malfunction etc.) a PET scan may need to be repeated or rescheduled. In such cases, subjects may be asked to stay for up to 48 h longer in each imaging session or repeat an imaging session at a later date. If the failure affects imaging session 1 before administration of radioactivity, the baseline scan may be repeated. If the failure affects imaging session 1 after administration of radioactivity, the baseline scan may be repeated once. If the technical failure affects imaging sessions 2 or 3 (after the subject has received an ASN51 dose), a third imaging session may be required, after a 7-day washout of the last dose of ASN51. Subjects will receive no more than 3 single doses of ASN51, or 3 doses of [F]-IMA601 during the study.
- Follow-up Visit or ET:** A follow up visit will be 7 days ( $\pm 3$  days) after the last on-treatment PET scan. Additional follow-up by telephone for any potential SAEs will be 28 days ( $\pm 3$  days) after the last on-treatment PET scan.
- Inpatient Stay:** Subjects will be admitted on Day -1 of imaging sessions 1, 2 and 3. Subjects will remain inpatient for both imaging sessions 2 and 3 for up to 72 h after dosing. In session 1, subject may leave the clinical unit in the evening of Day 1.
- MRI Questionnaire:** Subjects will complete an MRI questionnaire before the MRI scan, to exclude unsuitable subjects.

7. **MRI Scan:** Screening MRI will occur once all other screening results are available. If a subject is being re-screened (i.e. missed cohort) and there is already a recent MRI scan available within 3 months from their first screening period (ie if subjects were a reserve subject for a previous group but were not dosed and are no longer within the screening window) they do not need to have a repeat MRI scan.
8. **Venous cannulation:** One for administration of [F]-IMA601 (all imaging sessions) and one PK sampling (imaging sessions 2 and 3) (two venous cannulae be used).
9. **[F]-IMA601 Administration:** At the start of each PET scan.

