## 7.0 INVESTIGATIONAL PLAN

### 7.1 Study Design

This is an open-label, adaptive-design PET study to investigate the occupancy of O-GlcNAcase by ASN51 after single oral doses in healthy adult male and female subjects (aged 25-55 years, inclusive). The study schema is depicted in [Figure 2](#).

**Figure 2:** Phase 1a ASN51-102 Study Schema

Up to 10 subjects will be enrolled. Each subject will have up to 3 imaging sessions, with one scan in each session. In the first imaging session, subjects will have 240 ml of water followed by a baseline PET scan approximately 2 h later. In the second and third imaging sessions, subjects will receive a single oral dose of ASN51 with 240 ml of water, followed by an on-treatment PET scan. Safety and pharmacokinetic data of the SAD study ASN51-101 will be assessed by the SRC prior to the dosing of the first subject(s) to determine the first dose level to be administered in session 2 after the baseline session 1 and the timing of the PET scans in relation to the study drug administration time. At most 2 subjects will be dosed on the same study day. For subsequent sessions, the dose level and the time of the PET scan in all imaging session 2 and 3 will be determined after review of the results from the first on-treatment PET scan, including the PK data. Subjects will receive an intravenous dose of the radiolabelled tracer, [F]-IMA601, at the start of each PET scan.

This study will have an adaptive design: to adequately evaluate the exposure versus receptor occupancy (RO) relationship, various doses of ASN51 of up to 85% of the highest well-tolerated dose level in the preceding SAD study ASN51-101, and the timing of on-treatment PET scans may

be altered based on emerging data or study logistical requirements. On-treatment PET scans may be scheduled up to 48 h post-dose.

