After each on-treatment PET scan, the SRC will review available RO, PK, safety and tolerability data, before selecting the dose and PET scan timings for imaging session 3. Arterial blood sampling will be done during each PET scan to quantify the parent tracer related radioactivity over the course of the PET scan, and to establish a tracer metabolite corrected plasma input function. The total arterial blood volume required for each tracer injection will not exceed 145 mL. Arterial cannulation and arterial blood sampling may be reduced or removed if analysis of PET data from previous subjects indicates that noninvasive analysis of the PET scan data can be done. If a non-invasive analysis is not possible, the use of an arterial cannula with each PET scan will continue through the study.

Subjects will be screened within 21 days before their baseline PET scan. Their on-treatment PET scans will be within 7 days of their baseline scan with an interval of 7–14 days between imaging sessions 2 and 3. Subjects will be confined for 72 h after the study drug administration in sessions 2 and 3. After the baseline scan in session 1 without study drug administration, subjects may leave the unit in the evening. In the case of a technical failure (such as unsuccessful tracer synthesis), subjects may be asked to attend an additional on-treatment imaging session, in which they will receive a third oral dose of ASN51. There will be at least 7 days between each dose of ASN51. Subjects will not have more than 3 PET scans or 3 doses of ASN51 during the study. Subjects will have a follow-up visit at the research unit 7 days ( $\pm$  3 days) after imaging session 3 (Day 8).

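### The four-week SAE call is timed from the last scan or tracer dose, so it can come too early after an ASN51 dose that no scan follows

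*Protocol*

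**What the plan says.** Two places in the protocol set the date of the SAE telephone call.

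- Section 10.3.10: "Four weeks after last dose of tracer administration, an inquiry via phone will be done for the identification of potential SAEs".
- Table 1 notes, Follow-up Visit or ET: "Additional follow-up by telephone for any potential SAEs will be 28 days", with a window of ± 3 days, "after the last on-treatment PET scan".

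No passage times the call from ASN51. The secondary SAE endpoint (synopsis, Secondary Outcome Measures; SAP section 4.2.2) runs to four weeks after the last administration and does not say of which product.

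In sessions 2 and 3 the drug comes first and the scan second, and section 7.1 adds: "On-treatment PET scans may be scheduled up to 48 h post-dose". The Table 1 notes foresee a technical failure after ASN51 has been taken, for example an unsuccessful tracer synthesis. The remedies are optional: "subjects may be asked to stay for up to 48 h longer in each imaging session", or a session may be repeated later. Section 7.1 likewise says only that an additional session may be requested.

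**The concern.** ASN51 is the product under test, and the tracer is a non-IMP (section 9.8). The protocol uses the drug as its anchor elsewhere: contraception for women of child-bearing potential runs to 30 days after the last IMP dose (inclusion criterion 3), and dietary limits run to 72 h after the last study drug (section 9.10.5). The SAE call is tied to the scan or the tracer instead.

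If a subject takes ASN51 and no tracer injection or scan follows, the clock reverts to an earlier session. The active SAE inquiry then comes before four weeks have passed since the last exposure to ASN51. Any SAE arising after the call would be found only if the subject reported it unprompted (section 11.3). The period that the endpoint describes would not be actively covered, if that period is meant to run from ASN51.

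**Working it through.** This is calendar arithmetic. The inputs are:

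- call interval: 28 days ± 3 (Table 1 notes) or four weeks (section 10.3.10). Since 4 × 7 = 28, the two lengths agree;
- interval between sessions 2 and 3: 7 to 14 days (section 7.1). The Table 1 note on imaging admissions counts it to admission, with dosing the next day, which makes it 8 to 15 days to the dose;
- delay from dose to scan: 0 to 2 days (section 7.1);
- session 2: "Admission for imaging session 2 will be within 7 days after the baseline PET scan" (Table 1 notes).

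**Ordinary conduct.** Call after the last ASN51 dose = 28 + scan delay = 28 + 0 to 28 + 2 = 28 to 30 days. There is no shortfall.

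**Session-3 dose taken, no tracer, scan neither rescheduled nor repeated.** The last scan and last tracer dose are those of session 2. Call after the session-3 dose = 28 + session-2 scan delay − interval from session-2 dose to session-3 dose.

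| Session-2 scan | Interval 7–14 days | Interval 8–15 days (admission reading) |
|---|---|---|
| On the dosing day | 28 − 14 = 14 to 28 − 7 = 21 | 28 − 15 = 13 to 28 − 8 = 20 |
| 48 h after the dose | 30 − 14 = 16 to 30 − 7 = 23 | 30 − 15 = 15 to 30 − 8 = 22 |

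The main case is therefore 14 to 21 days, or 11 to 24 with the ± 3 day window, and the nominal range over all readings is 13 to 23. The shortfall against 28 days is 28 − 21 = 7 to 28 − 14 = 14 in the main case, and 28 − 23 = 5 to 28 − 13 = 15 over all readings.

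**Tracer injected in session 3, scan then fails** (a scanner malfunction is one of the failures listed in the Table 1 notes). Section 10.3.10 counts from the session-3 injection, which is correct. The Table 1 note counts from the last on-treatment scan, which may mean session 2 if an abandoned acquisition is not a scan. The two rules may then give different dates.

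**Session-2 dose taken, no tracer, subject stops.** There has been no on-treatment scan, so the Table 1 clock has no start. Section 10.3.10 counts from the baseline tracer dose (day 0). With the latest admission in Table 1 (day 7) and dosing on day 8, the call is 28 − 8 = 20 days after the dose, which is 8 days short.

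**The case against.** The strongest reply is that no harm is shown. The documents available give no ASN51 half-life, and the protocol accepts 7 days between doses, so 14 to 21 days after a single dose is two to three of those intervals. Subjects are confined for 72 h, have laboratory tests at 72 h, and are told to report events after discharge. In ordinary conduct the tracer comes after the drug, so the present anchor is the later and more cautious one. The failure also needs several things at once: after an untraced session 3 only two of the three permitted tracer doses have been used, so a make-up scan would usually be possible. The endpoint argument is conditional too, since last administration could be read as the tracer.

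All of this stands as a limit on importance. It does not make the rule right: the make-up scan is optional, a withdrawal between dose and scan rules it out, and nothing re-times the call. Section 7.4 allows six weeks for telephone follow-up within a participation of about 12 weeks, but that is a planning duration and supplies no anchor.

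Three stronger readings are tempting, and the documents do not support them.

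- A reader might infer that the follow-up visit also falls on or before the session-3 dose, because the synopsis times it "after receiving the last tracer dose" and the Table 1 note uses the last on-treatment scan. Taken alone, those words give 7 − 14 = −7 to 7 − 7 = 0 days relative to that dose. But the Table 1 grid places the visit after Visit 5, on Day 8. Day 4 carries the 72 h post-dose laboratory tests, so Day 1 is the dosing day and Day 8 is seven days after the dose. Section 7.1 and SAP section 5 agree, and sections 7.6.1 and 7.6.2 cover early termination.
- A reader might infer that the clocks go wrong only when no tracer is injected. The scanner-failure case shows otherwise.
- A reader might take the 28-day window in section 10.7.1 and put the untraced session-2 case as low as 28 − 21 = 7 days. That window conflicts with Table 1 and section 7.1, and section 10.0 refers to Table 1 for visit windows, so the figure should not be used.

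**Conclusion.** The point holds for the SAE call and only for the call. As written, the call falls nominally 14 to 21 days after an untraced, unrepeated session-3 dose of ASN51 (13 to 23 across readings), and about 20 days after an untraced session-2 dose at the latest Table 1 admission if the subject then stops. If the session-3 scan fails after injection, the two written clocks may disagree. The claim that the endpoint window is missed rests on reading last administration as ASN51, which the documents neither state nor exclude.

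The priority is low. The documents give no failure or withdrawal rate, but the contingency should be rare; at most 10 subjects are exposed, the other safety measures remain, and the primary endpoint is not affected. The follow-up visit is adequately dated already.

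**What to change.** In section 10.3.10 and the Table 1 note on follow-up, time the SAE call 28 ± 3 days from the later of the last ASN51 dose and the last tracer injection. Define last administration in the SAE endpoint (synopsis and SAP section 4.2.2) by the same anchor. Aligning the follow-up visit wording in the synopsis and the Table 1 note with section 7.1 would be tidying only.

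Taking the later of the two keeps the follow-up after the tracer and moves no date in ordinary conduct. In the untraced session-3 case the call moves 7 to 14 days later (5 to 15 across readings). In the untraced session-2 case it moves about 8 days later at the latest admission. Where the session-3 scan fails after injection, both rules then give one date. The cost is wording in a protocol amendment, which needs REC/MHRA approval before use (sections 13.1 and 13.1.1), and an update to a signed SAP. No visit or procedure is added.

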### **10.4 Clinical Laboratory Assessments**

Laboratory assessments will be used routinely to assess IMP safety in all subjects. After first administration of IMP, clinically significant abnormal laboratory findings must be documented as an AE. Samples will be collected as noted in the Schedule of Events (Table 1). Clinical laboratory parameters to be assessed for safety are listed in [Appendix A](#).

Fasting for a minimum of 4 hours prior to each blood draw is required and fasting status will be recorded. All clinical laboratory assessments will be conducted by the local laboratory unless otherwise specified. Communicate to the laboratory if the subject is receiving biotin supplements as high-dose biotin may interfere with certain laboratory assessments.

#### **10.4.1 Serum Chemistry**

Blood samples will be obtained for serum chemistry ([Appendix A](#)).

#### **10.4.2 Hematology**

Blood sample will be obtained for hematology (complete blood count with differential; [Appendix A](#)).

#### **10.4.3 Urinalysis**

A urinalysis panel (dipstick with microscopic examination on positives; [Appendix A](#)) will be obtained.

#### **10.4.4 Coagulation Panel(s)**

A coagulation panel will be obtained ([Appendix A](#)).

#### **10.4.5 Pregnancy Testing**

A negative serum pregnancy test is required from WOCBP within 24 hours before the first dose of IMP. Additional serum pregnancy tests (or urine pregnancy tests for MRI visit at [REDACTED]) will be obtained from females (WOCBP) at all subsequent clinic visits as noted in the Schedule of Events (Table 1).

All pregnancy tests will be performed at the site's local laboratory [REDACTED]. Pregnancy in subject or partner must be reported ([Section 11.6](#)); pregnant subjects will be discontinued from the trial.

#### **10.4.6 Serum Hormone Markers**

See [Appendix A](#)

### **10.5 Pharmacokinetic Assessments**

#### **10.5.1 Timing for Sampling**

See Table 1.

#### **10.5.2 Procedures for PK Blood Sampling**

About 2.0 mL blood for the PK samples will be collected via vena puncture or via an intravenous (i.v.) cannula placed following the local standard procedures. Information on equipment and further details on the procedures on the sampling are documented in a separate instruction manual.

#### **10.5.3 Shipping and Labeling**

Labeling and shipping instructions are provided in the Study Laboratory Manual.

#### **10.5.4 Bioanalysis**

The concentrations of ASN51 in plasma will be determined using a validated LC-MS/MS assay. In addition, urine samples may be analyzed for occurrence of metabolites of ASN51 with an exploratory method if warranted.

### 10.5.5 Pharmacokinetic Parameters

The plasma PK parameters for ASN51 will be derived by non-compartmental analysis of the plasma concentration-time profiles at the end of study only.

The following pharmacokinetic parameters are defined:

- The area under the plasma concentration-time curve from time zero to time  $t$  of the last measured concentration above the limit of quantification ( $AUC_{0-t}$ ).
- The area under the plasma concentration-time curve from zero to infinity ( $AUC_{0-\infty}$ ).
- The maximum plasma concentration ( $C_{max}$ ).
- The time to reach maximum plasma concentration ( $t_{max}$ ).
- The terminal elimination rate constant ( $\lambda_Z$ ) with the respective half-life ( $t_{1/2}$ )
- The percentage of the extrapolated AUC.

$AUC_{0-t}$  will be calculated according to the linear up/log down trapezoidal method using the measured concentration-time values above the limit of quantification (LOQ).  $AUC_{0-\infty}$  will be calculated by combining  $AUC_{0-t}$  and  $AUC_{extra}$ .  $AUC_{extra}$  represents an extrapolated value obtained by  $C_t/\lambda_Z$ , where  $C_t$  is the last plasma concentration measured above the LOQ and  $\lambda_Z$  represents the terminal elimination rate constant determined by log-linear regression analysis of the measured plasma concentrations of the terminal elimination phase. The half-life will be calculated as follows:  $t_{1/2} = \ln 2 / \lambda_Z$ .

The  $C_{max}$ , and time to peak concentration ( $t_{max}$ ) will be directly determined from the observed plasma concentrations data.  $AUC_{0-t}$  will be calculated using linear up/log down trapezoidal method using the measured concentration-time values above the limit of quantification (LOQ).

All PK parameters will be based on actual blood sampling times [h] (relative to the corresponding administration time) rounded to two digits and negative pre-dose times will be set to zero.

### 10.6 Total volume of blood removed

Hematology:  $7 \times 2\text{mL} = 14\text{ mL}$

Clinical Chemistry:  $7 \times 3.5\text{mL} = 24.5\text{ mL}$

Coagulation:  $7 \times 3\text{mL} = 21\text{ mL}$

FSH, Serology:  $1 \times 3.5\text{ mL} = 3.5\text{ mL}$

Pregnancy Test\*:  $4 \times 3.5\text{ mL} = 14\text{mL}$

PK:  $32 \times 2\text{ mL} = 64\text{ mL}$

Arterial blood:  $3 \times 145\text{ mL} = 435\text{mL}$

Total:  $576\text{ mL}$  within about 4-6 weeks

\*included in serology sample at screening

If a study session is repeated because of a PET scan failure, an extra 53 mL of blood may be taken during the whole study.

No more than an extra 50 mL of blood will be taken from any subject.

## 10.7 Instructions for PET Scans

### 10.7.1 General Procedures

If arterial cannulation will be used, the patency of subjects' ulnar and radial arteries in both wrists will be checked, at screening and before insertion of the arterial cannula on scanning days (Allen's test). Up to 10 subjects will be enrolled. At most 2 subjects will be dosed in parallel. Each subject will have up to 3 imaging sessions, with one scan in each session. In the first imaging session, subjects will have 240 ml of water followed by a baseline PET scan approximately 2 h later. In the second and third imaging sessions, subjects will receive a single oral dose of ASN51 with 240 ml of water, followed by an on-treatment PET scan.

The study will have an adaptive design: to adequately evaluate the exposure versus RO relationship, various doses of ASN51 up to 85% of the highest well-tolerated dose in the SAD study ASN51-101 may be tested, and the timing of on-treatment PET scans may be altered based on emerging data or study logistical requirements. On-treatment PET scans may be scheduled up to 48 h post-dose. Before each on-treatment PET scan, the SRC will review available RO, PK, safety and tolerability data, before selecting the dose and PET scan timings for all on-treatment imaging sessions. Subjects will receive an intravenous dose of the radiolabelled tracer, [F]-IMA601, at the start of each PET scan.

Arterial blood sampling will be done during each PET scan to quantify the parent tracer related radioactivity over the course of the PET scan, and to establish a tracer metabolite corrected plasma input function. The total arterial blood volume required for each tracer injection will not exceed 145 mL. Arterial cannulation and arterial blood sampling may be reduced or removed if analysis of PET data from previous subjects indicates that noninvasive analysis of the PET scan data can be done. If a non-invasive analysis is not possible, the use of an arterial cannula with each PET scan will continue through the study.

Subjects will be screened within 21 days before their baseline PET scan. Their on-treatment PET scans will be within 28 days of their baseline scan with an interval of 7–14 days between imaging sessions 2 and 3. Subjects will be confined from Day -1 until about 72 h after drug intake in on-treatment sessions 2 and 3. In session 1, subjects will be confined from day -1 and may leave the clinical unit in the evening of the PET scan on Day 1. In the case of a technical failure (such as unsuccessful tracer synthesis), subjects may be asked to attend an additional on-treatment imaging session, in which they will receive a third oral dose of ASN51. There will be at least 7 days between each dose of ASN51. Subjects will not have more than 3 PET scans or no more than 3 doses of ASN51 during the study.

